I. Administrative information:

Title:

Accuracy of linear measurements of ultra-low dose Cone Beam Computed Tomography and Digital Panoramic Radiography Performed on mandibular anaesthetic landmarks Versus Real mandibular measurements (Diagnostic Accuracy Study)

II. Introduction:

Background:

One of the important mandibular anatomical landmarks is the inferior alveolar Nerve which can be damaged during surgical procedures such as third molar extraction, management of trauma and surgical removal of tumors. Therefore the dentist must be able to localize it prior to any dental procedure (Patil et al 2015).

The mandibular foramen represents the entrance of the inferior alveolar nerve, which passes through the mandibular canal throughout the body of the mandible till it reaches the mental foramen where it divides into mental nerve and incisive nerve (Salinas et al 2016).

In the past, the anterior region of the mandible was regarded as a safe area for implant surgery due to the absence of neurovascular structures. However, recent studies have shown haemorrhage and hematoma formation in the floor of the mouth due to injury to the vessels of the mandibular lingual foramen (Rosano et al 2009).

Panoramic radiography is simple, inexpensive, and widely used, in addition to offering low radiation exposure to the patient. Kaffe et al 1994 found panoramic radiographs to be beneficial in locating mandibular foramen. In another study performed by Kositbowornchai et al 2007 it was found that there is a high accuracy between the distances measured on panoramic radiographs and real measurements on dry mandibles (Kaffe et al 1994) and (Kositbowornchai et al 2007).

Ultra-Low Dose CBCT technology is a recommended option for clinicians due to the decrease in radiation exposure to patients. Patients must not be exposed to a higher dosage than needed to acquire images of sufficient diagnostic quality (Kusnoto et al 2015)

Review of literature:

Resources: PubMed, Science direct.

In a study performed on dry mandibles the comparison of linear measurements made with digital caliper and CBCT showed no significant differences for 95% of the distances measured. The 5% discrepancy is considered acceptable (Kamburoglu et al 2011) and (Sanjana et al 2017).

A study was performed to evaluate the accuracy of panoramic radiographs in the localization of mandibular foramen on dry mandibles, where the position of mandibular foramen in relation to the ramus width and height was noticed. The results showed that there were statistically significant differences between distances measured on dry mandibles and radiographs except for the upper anterior ramus height (**Kositbowornchai et al 2007**) and (**Patil et al 2015**).

Another study was conducted on dry mandibles for the localization of the mental foramen. Measuring the distances from the crest of the ridge to the center of the mental foramen and from the inferior border of the mandible to the center of the mental foramen in addition to the location of the mental foramen relative to its' alignment with mandibular teeth. For mental foramen measurement from crest of the ridge till its' center did not show a significant difference for laterality, while the distance from the inferior border of the mandible till the center of the mental foramen the results showed a significant difference. Studies have shown that the most common location of the mental foramen is aligned with the second premolar, followed by between the first and the second mandibular premolar (**Lopes et al 2010**).

A study was performed for the localization of the lingual foramen using CBCT. Linear measurements were made including their diameter, the distance between the lingual foramen and the crest of the ridge and the distance from the inferior border of the mandible to the lingual foramen. Lingual foramina were classified according to their location into midline type, Para median type or posterior type. (**He et al 2016**).

CBCT and panoramic radiographs have been used to detect and measure lingual foramina. It has been proposed that CBCT provides highly accurate data of the mandibular anatomy (**Ludlow et al 2007**) and (**Stratemann et al 2008**).

III. Methods:

A. The pre-analytical phase: Mandibular anaesthetic landmarks will be identified on each dry mandible and will be marked using gutta percha.

B. The analytical phase. The ten human dry mandibles will be submitted for:

1-Digital Panoramic Radiography.

Panoramic radiographs will be obtained using the SOREDEX CRANEX™ 3Dx unit. The exposure parameters will be 8Ma, 63kVp and 16.4 sec exposure time.

2-Cone Beam Computed Tomography (CBCT).

SOREDEX CRANEX™ 3Dx unit will be used in this study. Images will be acquired at a single rotation. SOREDEX® MiniDose parameters will be used. The exposure parameters will be 3.2 Ma, 90kVp and 2.3 sec exposure time to take the advantage of 3D data in dose sensitive cases like children, or reduce the radiation dose for the patient.

The real linear measurements will be measured in millimeter on dry mandibles using digital caliper and will be compared with measurements obtained from both techniques.

C. The post analytical phase. Images will be evaluated by two experienced radiologists of ten years of experience. Each one will evaluate the images separately twice with a period of two weeks in-between the two reading sessions. The researcher will measure out the real linear measurements on the dry mandibles using digital caliper.

D) Statistical analysis

Sample size calculation and how it was determined

Sample size calculation was done using R statistical package, version 3.3.1 (21-06-2016). Copyright (C) 2016. The R Foundation for Statistical Computing.

One-way analysis of variance power calculation for more than two groups was used to detect the proper sample size. Means and standard deviations were determined according to Patil et. al (2015) based on the difference in distances measured on dry mandibles between different radiographic techniques.

The results showed that, at a power of 80% and a two-sided significance level of 5%; a total sample size of 10 dry mandibles will be adequate to reject the null hypothesis that the group means are equal; i.e there's no difference between radiographic techniques.

Sample Size Calculation statistical output

Name of the test: One-way analysis of variance (ANOVA) power calculation for more than two groups.

Source use for calculation:** Patil et. al, 2015

Output:

```
> m1=15.27
> sd1=1.57
> m2=16.93
> sd2=1.54
> n1=n2=25
> k=2
> within.var=(sd1^2+sd2^2)/2
> m=((n1*m1)+(n2*m2))/(n1+n2)
> between.var=(((m-m1)^2)+((m-m2)^2))/(k-1)
> power.anova.test(groups = 3, between.var = between.var, within.var =
within.var, power=0.80, sig.level=0.05)
```

Balanced one-way analysis of variance power calculation

groups = 3

n = 9.52841

between.var = 1.3778

within.var = 2.41825

sig.level = 0.05

power = 0.8

NOTE: n is number in each group

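### Section D states no analysis of the four readings per image; its only method, a one-way ANOVA used for the sample size, ignores the pairing and tests equal means, not accuracy

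*Combined protocol and SAP*

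**What the plan says.** The title sets the question: "Accuracy of linear measurements of ultra-low dose Cone Beam Computed Tomography and Digital Panoramic Radiography", judged against real mandibular measurements.

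- **Specimens (Methods, B).** "The ten human dry mandibles will be submitted for" both panoramic radiography and CBCT. Caliper values are taken on the same mandibles and "will be compared with measurements obtained from both techniques". No statistic is named for that comparison.
- **Readings (Methods, C).** There are two radiologists, and "Each one will evaluate the images separately twice with a period of two weeks in-between the two reading sessions". That is 2 × 2 = 4 values per image.
- **Section D.** It contains only the sample size. "One-way analysis of variance power calculation for more than two groups was used to detect the proper sample size", and the conclusion is that "a total sample size of 10 dry mandibles will be adequate to reject the null hypothesis that the group means are equal". The R output has three groups, "within.var = 2.41825", n = 9.52841 and the line "NOTE: n is number in each group".

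Nowhere does the document say how four readings become one value, how repeat readings or readers are compared, or which paired or agreement statistic sets image against caliper. Section D runs from its heading to complete R output, so no redaction or lost text explains the gap.

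**The concern.** The design is paired: each mandible gives three sets of values, two of them read four times. The only hypothesis and method in the plan belong to a different design, three unrelated groups with one value per specimen. That model has no mandible, reader or repeat term.

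Two things are at stake. First, an unpaired comparison counts natural differences in mandible size as error, so a real bias of a technique against the caliper can be missed. Second, equal means is a weaker property than accuracy. A technique can be right on average and still scatter widely around the caliper value, and a finding of no difference could then be presented as accuracy. The planned repeat readings could describe that scatter and the readers' agreement, but no output is planned for either.

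**Working it through.** **1. The plan's own figure.** Inputs from the R code in section D: means 15.27 and 16.93, SDs 1.57 and 1.54.

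- Within variance = (1.57² + 1.54²)/2 = 2.41825. Between variance from the two means (midpoint 16.10, k = 2) = 0.83² + 0.83² = 1.3778. Both match.
- Noncentral F with λ = (g−1)·n·between/within, df g−1 and g(n−1), g = 3, α = 0.05, power 0.80 gives n = 9.5284 per group (stated 9.52841). At n = 10 power is 82%.
- The error df g(n−1) are those of independent groups, with no within-mandible correlation. The words independent groups are not in the document; they follow from the R call and its reproduced output.

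**2. What happens if that test becomes the analysis.** The documents give no technique, reading or caliper SD, so these are assumed: reading SD 0.3 mm, caliper SD 0.15 mm, mandible-specific technique SD as shown. Readings are averaged per image. Mandible variance = 2.41825 − technique SD² − 0.3²/4, so the two imaging groups keep variance 2.41825. There are 20,000 simulated trials per row, ten mandibles, α = 0.05, and a shift of 16.93 − 15.27 = 1.66 mm in one technique. RM is repeated-measures ANOVA with Greenhouse-Geisser correction.

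| Technique SD (mm) | One-way, true null | RM, true null | One-way, 1.66 mm | RM, 1.66 mm |
|---|---|---|---|---|
| 0.3 | 0.0% | 4.1% | 67.0% | 100% |
| 0.5 | 0.0% | 4.5% | 68.1% | 100% |
| 1.0 | 0.3% | 4.4% | 72.4% | 97.5% |
| 1.5 | 5.25% | 4.6% | 77.8% | 72.6% |

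In this construction the caliper group's variance (mandible variance + 0.15²) is not held constant. It is 2.33, 2.17, 1.42 and 0.17 down the rows. The last row, where the loss disappears, therefore implies a caliper SD of 0.41 mm. If mandible variance is instead kept at 2.41825, one-way power is 64.1, 59.8, 46.7 and 34.7%, against 100, 100, 97.5 and 73.1% for RM.

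**3. Separating out another cause.** The code takes the between variance from two means but runs with three groups. For a true pattern of 0, 1.66, 0 the between variance is 0.9185, and for 0, 1.66, 0.83 it is 0.6889. With fully independent groups of ten, power is then 64% and 51%. So much of the gap between 67 to 72% and the planned 80% is not due to ignoring pairing. The cost of ignoring pairing is the contrast with RM within each row.

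**4. Equal means against accuracy.** With no mean bias, true single-reading limits of agreement are ±1.96·√(technique SD² + 0.3² + 0.15²) = ±0.88, ±1.18 and ±2.07 mm at technique SD 0.3, 0.5 and 1.0. The equal-means tests in the table reject in at most 5% of trials in all three cases, so a non-significant result does not tell them apart.

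**The case against.** The strongest reply is that the ANOVA is named only for the sample size. That is correct. A reader might infer that the plan commits to a one-way ANOVA as its analysis, but the text does not say so, and the losses in the table apply only if the test is carried over. What stands is that section D names nothing else, so the analysis would be chosen after the data are seen.

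A reader might also infer that the 40 image-minus-caliper differences will be treated as independent. Nothing in the document proposes this, so it is only a caution. If it were done, with no caliper error and reading SD 0.1 to 1.0 mm, type I error would be about 8 to 36% at technique SD 0.3 to 1.0, and about 5% at technique SD 0.

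Nor do the documents support saying that readings would typically miss by 2 mm. Under the assumptions above, the share of single readings off by more than 2 mm is 5.8% at technique SD 1.0, 0.09% at 0.5 and about 0.001% at 0.3, and no figure in the plan supports 1.0.

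The SDs are assumed, and the power loss depends on them. The missing analysis and the mismatch between equal means and accuracy do not.

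**Conclusion.** The point holds as an unstated analysis whose only named method does not fit the design. Carried into the analysis, that method would be conservative and underpowered, not prone to false positives. At technique SD 0.3 to 1.0 mm, with reading SD 0.3, caliper SD 0.15 and imaging-group variance 2.41825, it rejects a true null in under 0.5% of trials. It finds a 1.66 mm shift in about 67 to 72%, against 97 to 100% for a repeated-measures test. The full distance from 80% should not be blamed on pairing, because the two-mean, three-group input accounts for part of it. The n of 9.52841 also follows from its stated inputs and is not an arithmetic error. Whatever the SDs, a test of equal means does not answer the title's question. This should be changed before the data are analysed.

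**What to change.** State the following in section D, for each distance:

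1. Average the four readings per mandible and technique. Analyse image-minus-caliper differences with the mandible as the unit. If both sides are measured, keep the mandible as the unit or add a side term.
2. For each technique, report the mean difference with its 95% interval (9 df) and the limits of agreement with intervals.
3. Limits from averages are too narrow for one reading. Take single-reading limits from the balanced mean squares: variance = MS(mandible)/4 + MS(reader-by-mandible)/4 + MS(repeat)/2, with 9, 9 and 20 df. With T, R and e the mandible-level, reader-by-mandible and repeat variances, the expected mean squares are 4T+2R+e, 2R+e and e, so the sum is T+R+e. These df assume one value per distance per mandible.
4. Compare panoramic with CBCT by the paired difference of mandible means.
5. Report the intra-reader SD from the within-reader repeats and the mean difference between readers with its interval.
6. Rule out an independent-groups one-way ANOVA, and rule out treating the four readings as independent observations.

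A large mixed model is not needed for ten mandibles in a balanced design.

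**Cost:** wording and a little more analysis work, with no extra specimens, exposures, readers or readings. Intervals will be wide: the 95% interval for a mandible-level SD runs from 0.69 to 1.83 times the estimate, and for an intra-reader SD from 0.77 to 1.44 times. They should be reported as such.

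### The sample size of ten mandibles and its 80% power come from a one-way ANOVA for three independent groups, but the same mandibles are measured by all three methods

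*Combined protocol and SAP*

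**What the plan says.** Section III.B describes a matched design. "The ten human dry mandibles will be submitted for" panoramic radiography and CBCT, and the caliper values taken on the dry mandibles "will be compared with measurements obtained from both techniques". Each mandible therefore supplies a caliper, a panoramic and a CBCT value.

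Section III.D sizes the study differently: "One-way analysis of variance power calculation for more than two groups was used to detect the proper sample size". In the printed R output the error variance is "within.var=(sd1^2+sd2^2)/2", the average of two group variances. The between-group variance is computed from two means with k=2. The call is "power.anova.test(groups = 3, between.var = between.var, within.var", with 80% power and a 5% significance level. The result is n = 9.52841, with the line "NOTE: n is number in each group". The text then concludes that "a total sample size of 10 dry mandibles will be adequate to reject the null hypothesis that the group means are equal".

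The plan does not label the three groups; they are read here as caliper, panoramic and CBCT. Section D contains only the sample size calculation. It names no analysis, and it does not say that one-way ANOVA will be the analysis.

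**The concern.** A one-way ANOVA power calculation treats every value as coming from a different mandible, so its error term includes all the variation in size between mandibles. When each mandible is measured by every method, that variation cancels from the comparison. The error that matters is then the spread of within-mandible differences, and the plan supplies neither that SD nor a correlation from which to derive it. The 80% is thus a property of 10 mandibles in each of three separate groups, 30 in all, and not of ten mandibles measured three ways.

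At stake is whether ten mandibles are enough, and how precisely each technique's error against the caliper will be estimated. The plan as written answers neither question.

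**Working it through.** **Inputs, all from the R output in Section III.D.** Means 15.27 and 16.93 (difference 1.66 mm); SDs 1.57 and 1.54; groups = 3; alpha 0.05; power 0.80. The within-mandible correlation r is not given, so it is assumed and varied. All figures take one value per mandible per method, with equal variances and equal correlations.

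**1. The plan's own figure.**
- Within-group variance: (1.57² + 1.54²)/2 = 2.41825.
- Between-group variance: the grand mean is 16.10, so 0.83² + 0.83² = 1.3778 (divisor k−1 = 1).
- Noncentral F with df 2 and 3(n−1), λ = 2·n·1.3778/2.41825. Power of 80% gives n = 9.53 per group; at n = 10 per group the power is 82.2%.

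The printed result reproduces, for three independent groups.

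**2. What the between-group variance should be for three means.** If three means span 1.66 mm, their variance is:
- 1.66²/3 = 0.9185 when two of them coincide (the maximum);
- 1.66²/4 = 0.6889 when the third lies midway.

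To reach 1.3778, three means must span √(3 × 1.3778) = 2.03 mm to √(4 × 1.3778) = 2.35 mm.

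**3. Matched design, repeated-measures ANOVA, ten mandibles.** Noncentral F with df 2 and 18, λ = 2·10·(between-group variance)/[2.41825·(1−r)].

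| Between-group variance | r = 0 | r = 0.3 | r = 0.5 | r = 0.8 | r needed for 80% |
|---|---|---|---|---|---|
| 1.3778 (plan) | 79.9% | 92.2% | 98.1% | >99.9% | about 0 |
| 0.9185 | 61.5% | 77.8% | 90.3% | 99.9% | 0.34 |
| 0.6889 | 48.8% | 64.7% | 79.9% | 99.5% | 0.50 |

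**4. One technique against the caliper, paired t-test, 1.66 mm, n = 10.** SD of differences = √[2 × 2.41825 × (1−r)]. For 80% power:
- at alpha 5%, r of about 0.43 (SD of differences at most 1.67 mm);
- at alpha 2.5%, for two comparisons against the caliper, r of about 0.56 (at most 1.46 mm).

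**5. Precision.** The 95% CI half-width for a mean difference is t(0.975, 9) × SD/√10, with t = 2.262.

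| r | SD of differences (mm) | Half-width (mm) |
|---|---|---|
| 0 | 2.20 | 1.57 |
| 0.3 | 1.84 | 1.32 |
| 0.5 | 1.56 | 1.11 |
| 0.8 | 0.98 | 0.70 |
| 0.9 | 0.70 | 0.50 |

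**The case against.** The strongest reply is that ignoring the matching does no harm. At the plan's inputs, matched power is 79.9% with no correlation and rises with any positive correlation. All three methods measure the same distances between landmarks marked on the same bones, so a high correlation is plausible; at r = 0.7, power is about 96% or more in every row of the repeated-measures table. Every repeated-measures figure below 79.9% comes from the two-mean variance being used for three groups, which is a separate input error. The 0.9185 ceiling also assumes that the third mean lies within the 1.66 mm span, which the plan does not say. Finally, two radiologists each read twice, and averaging their readings would reduce the error.

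Much of this stands. The mismatch alone does not show that the study is too small, the ceiling is conditional, and high correlation may well hold. But the reassurance at the plan's inputs needs the 1.3778, so the two errors cannot be separated when asking whether ten mandibles suffice. The reassurance also covers only the overall F test: even at the plan's 1.66 mm, the paired comparison with the caliper needs r of about 0.43 or more. The plan states no correlation, no third mean and no rule for combining readings, so a favourable value of any of them is the reader's assumption.

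**Conclusion.** The concern holds. The stated 80% was computed for three independent groups, and no quantity in the plan converts it to ten mandibles measured three ways. Correcting the model alone leaves power at about 80% or better. Correcting the between-group variance as well, for three means spanning 1.66 mm, gives anything from 49% (r = 0, third mean midway) to over 99% (r = 0.8), so adequacy turns on an unstated correlation of roughly 0.34 to 0.50. The expected CI half-width varies about threefold, from 1.57 to 0.50 mm, as r goes from 0 to 0.9.

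This should be fixed; it is not proof of an underpowered study. The conclusion rests on reading the three groups as the three methods, and the figures rest on the assumptions listed with the inputs.

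**What to change.** Restate the power for n = 10 on the SD of within-mandible differences. Give the assumed SD or correlation with its source, and show a range. Use either a between-group variance computed from three stated means, or a single paired difference with the alpha that applies to two comparisons against the caliper. Label the groups.

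Name an analysis matched by mandible to which that power refers: technique-minus-caliper differences with confidence intervals, repeated-measures ANOVA, or a mixed model with a random mandible effect. Say how the repeated readings enter it.

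The cost is a few sentences and one rerun of the calculation. The restatement itself needs no extra mandibles, but its result may or may not support 80% with ten, and the plan should report whichever it is.

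### The title promises accuracy against caliper distances, but the only hypothesis stated is equal group means under an independent-groups ANOVA, which cannot show accuracy

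*Combined protocol and SAP*

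**What the plan says.** The title sets the question: "Accuracy of linear measurements of ultra-low dose Cone Beam Computed Tomography and Digital Panoramic Radiography" is to be judged against real mandibular measurements, and the study is labelled a diagnostic accuracy study.

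III. Methods, section B, gives the design: "The ten human dry mandibles will be submitted for" panoramic radiography and CBCT. The researcher also measures the same bones with a digital caliper, and these values "will be compared with measurements obtained from both techniques". How they will be compared is not said.

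Section C has two radiologists reading the images: "Each one will evaluate the images separately twice with a period of two weeks in-between the two reading sessions". No rule turns these four readings into one value, and no repeatability statistic is named.

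Section D (Statistical analysis) contains only the sample size. It says that "One-way analysis of variance power calculation for more than two groups was used to detect the proper sample size", and that "a total sample size of 10 dry mandibles will be adequate to reject the null hypothesis that the group means are equal". It then explains this null as the radiographic techniques not differing from one another. The R call uses three groups without saying what they are. No other test, model or estimate appears in the document.

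**The concern.** The stated hypothesis and the title's question do not meet at three points.

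- **Reference.** Accuracy is distance from the caliper value. The null, as the plan explains it, compares radiographic techniques with each other. Two techniques could agree and both be wrong.
- **Measure.** Equal means say nothing about the size of error on a single mandible, since positive and negative errors cancel. An overall F test also does not show which method departs.
- **Structure.** All methods measure the same ten mandibles, so the data are paired. The formula is for independent groups.

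The background motivates the study by nerve injury and haemorrhage from vessel injury, so the error in millimetres is the result that matters. If only the named method were followed, the study would give no such figure, and nothing in the plan prevents a non-significant result from being read as accuracy.

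**Working it through.** **1. The plan's own figure.** Inputs from the R output in section D: means 15.27 and 16.93, SDs 1.57 and 1.54, three groups, 80% power, 5% level.

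- Within-group variance: (1.57² + 1.54²)/2 = (2.4649 + 2.3716)/2 = 2.41825, so SD = 1.555 mm.
- Between-group variance: the overall mean is 16.10, and 0.83² + 0.83² = 1.3778.
- Noncentral F with λ = (3 − 1) × n × 1.3778/2.41825 and 2 and 3(n − 1) df gives n = 9.528 for 80% power. The plan prints 9.52841, so the figure reproduces. At n = 10 the power is 82.2%.

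The n follows from its inputs. The issue is what the formula tests.

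**2. Equal means without accuracy.** Take ten errors alternating +2 and −2 mm. Their mean is 0, so a paired t is 0. Their SD is √(40/9) = 2.108 mm, so the 95% limits of agreement are ±1.96 × 2.108 = ±4.13 mm.

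**3. What independence costs (illustration).** Assume the independent-groups ANOVA is the final analysis, with three methods on ten mandibles, one of them biased by 1 mm, SD 1.555 mm for each, and a common within-mandible correlation r. The r values are assumptions; the documents give none.

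- SD of differences: SDd = 1.555 × √(2(1 − r)).
- Under the null, the ANOVA numerator has expectation σ²(1 − r) and the denominator σ², so the test becomes conservative as r rises.
- At r = 0, λ = 2 × 10 × (1/3)/2.41825 = 2.757 and power is 27.0%. For r above 0 the ANOVA figures are simulated (400,000 runs). The paired t figures use the noncentral t with 9 df and noncentrality √10/SDd.

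| r | SDd (mm) | ANOVA, 1 mm bias | ANOVA, type I error | Paired t, 1 mm bias | 1.96 × SDd (mm) |
|---|---|---|---|---|---|
| 0.5 | 1.555 | 17.7% | 0.6% | 44.3% | 3.05 |
| 0.8 | 0.984 | 11.3% | 0.02% | 81.6% | 1.93 |
| 0.9 | 0.695 | 9.1% | <0.01% | 98.1% | 1.36 |
| 0.95 | 0.492 | 8.0% | <0.01% | >99.9% | 0.96 |

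The last column shows why pairing alone is not enough. With zero mean bias the paired test is non-significant 95% of the time at every r, while the limits of agreement run from ±0.96 to ±3.05 mm.

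**4. Precision at n = 10.**

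- Mean bias, 95% CI half-width: 2.262/√10 = 0.715 × SDd, which is 0.35 mm (r = 0.95) to 1.11 mm (r = 0.5).
- Each limit of agreement, exact 95% CI: take the 0.975 and 0.025 quantiles of the noncentral t with 9 df and noncentrality 1.96 × √10, and divide by √10. This gives 3.80 and 1.16. The interval therefore extends 3.80 − 1.96 = 1.84 × SDd outward and 1.96 − 1.16 = 0.80 × SDd inward. Outward that is 0.91 to 2.86 mm for r = 0.95 to 0.5.
- The usual symmetric approximation gives 2.262 × √(1/10 + 1.96²/18) = 1.27 × SDd, an outer bound of 3.23 rather than 3.80 × SDd. It is too narrow outward at this n and should not be used.

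**The case against.** The strongest reply is that section D uses the ANOVA to size the study and never declares it as the final analysis. That is right. A reader might infer that the plan commits to an independent-groups ANOVA and so will miss most real biases, but the documents do not support this. The detection rates and type I errors above describe a hypothetical analysis. They also rest on assumed correlations and on equal SDs and correlations across methods, for which the documents give no evidence. What stands is that no other hypothesis or method is stated, and the one stated does not address the caliper.

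The meaning of the SD can also be disputed. Section D says its inputs are based on differences in distances between techniques. I have read 1.57 and 1.54 mm as spread between mandibles. If 1.555 mm is instead the SD of differences, the paired figures in the r = 0.5 row apply and the ANOVA figures have no basis.

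A reader might also take the literature review as setting the acceptance standard. It reports of earlier work that "comparison of linear measurements made with digital caliper and CBCT showed no significant differences for 95% of the distances measured" and adds that "The 5% discrepancy is considered acceptable". This describes other studies, and the plan does not adopt it. It would not serve in any case, since it counts significance tests and gives no error in millimetres.

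Finally, a tolerance rule, or separate limits for single readings, is a preference and not a necessity. I accept that and do not require either.

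**Conclusion.** The concern holds in this form: the only stated hypothesis and method cannot answer the title's question, and no measure of error or agreement against the caliper is specified. That conclusion comes from the text and needs no assumed number. It should be corrected before the images are read.

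The size is illustrative. With SD 1.555 mm, n = 10 and r assumed between 0.5 and 0.95, carrying the ANOVA into the final analysis would detect a 1 mm bias in one method in about 18% to 8% of studies, with type I error of about 0.6% or less instead of 5%. A paired t test would detect it in 44% to over 99%. The sample-size arithmetic reproduces, so this is not a calculation error. Nor do the documents show that an unsuitable final analysis has been chosen; they show that none has been stated.

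**What to change.** In section D:

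- For each technique and distance, make the paired signed error (technique minus caliper) per mandible the primary measure. State how the four readings are combined, for example by their mean.
- Report mean bias with its 95% CI, and 95% limits of agreement with exact (noncentral t) 95% CIs.
- Report intra- and inter-reader repeatability separately.
- State that a non-significant difference will not be read as accuracy.
- Replace the ANOVA power statement with the precision at ten mandibles: 0.72 × the SD of differences either side of the mean bias; for each limit of agreement, about 1.84 × that SD outward and 0.80 × inward (outer bounds: mean ± 3.80 × SD).

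The cost is a little more analysis and no new data. The investigators must also accept that ten mandibles give an estimate of error with wide limits. If they want to claim acceptable accuracy, the tolerance in millimetres is theirs to choose and must be fixed before reading begins.

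### The 80% power stated for 10 mandibles does not follow from the calculation's own inputs, and it does not address each technique against the caliper

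*Combined protocol and SAP*

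**What the plan says.** The title sets the question as the accuracy of two imaging techniques "Performed on mandibular anaesthetic landmarks Versus Real mandibular measurements". Methods, part B, repeats it: the caliper values "will be compared with measurements obtained from both techniques". The design is paired, because "The ten human dry mandibles will be submitted for" both panoramic radiography and CBCT, and the caliper is applied to the same bones. Part C adds two readers: "Each one will evaluate the images separately twice with a period of two weeks in-between the two reading sessions".

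Part D, Statistical analysis, holds only a sample size calculation. It states that "One-way analysis of variance power calculation for more than two groups was used to detect the proper sample size", and it ties 80% power at a two-sided 5% level to the null that "the group means are equal; i.e there's no difference between radiographic techniques". The R output enters two means (15.27 and 16.93), two standard deviations (1.57 and 1.54) and k = 2. It forms the between-group variance in the line that begins "between.var=(((m-m1)^2)+((m-m2)^2))/(k-1" and passes it to the call that begins "power.anova.test(groups = 3, between.var = between.var". The result is n = 9.52841 per group, taken as 10 mandibles. Neither part D nor any other section names a test, interval or agreement measure for either technique against the caliper.

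**The concern.** Three things separate the 80% figure from the study that is described.

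- **Input mismatch.** The between-group variance is computed from two means but used as the variance of three. No third mean is given.
- **Independence.** One-way ANOVA treats the groups as separate samples. Here each mandible contributes a panoramic, a CBCT and a caliper value, so the precision of a comparison depends on the within-mandible correlation, which the plan does not give.
- **Target.** Taking the three groups to be panoramic, CBCT and caliper, rejection would show that the means are not all equal. It would not show which technique departs from the caliper, or by how much.

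The reader therefore cannot tell how the accuracy comparison will be made or how precisely 10 mandibles can estimate it. With two readers and two sessions per image and no stated analysis, the choice of reading and method also stays open after the data are seen.

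**Working it through.** **Inputs from part D:** means 15.27 and 16.93; SDs 1.57 and 1.54; k = 2; groups = 3; alpha 0.05; power 0.80. Units are taken as millimetres, as for the caliper.

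**1. Reproducing the plan's figure.**
- Difference: 16.93 − 15.27 = 1.66; each mean lies 0.83 from their midpoint.
- Within-group variance: (1.57² + 1.54²)/2 = 2.41825, so SD = 1.555.
- Between-group variance: (0.83² + 0.83²)/(2 − 1) = 1.3778.
- Balanced one-way ANOVA power uses the noncentral F with λ = (groups − 1) × n × between/within and df = (groups − 1, groups × (n − 1)).
- With 3 groups, 80% power needs n = 9.528, which agrees with the plan. At n = 10, λ = 2 × 10 × 1.3778/2.41825 = 11.40 and power is 82.2%.

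**2. What 1.3778 means with three groups.**
- Two means equal, one at distance d: variance = d²/3, so d = √(3 × 1.3778) = 2.03 mm.
- Equally spaced over range R: variance = (R/2)², so R = 2 × √1.3778 = 2.35 mm.
- Either way the range exceeds the 1.66 mm from which the variance was built.

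**3. Omnibus power if 1.66 mm is the range of the three means (n = 10 per group, same within-group variance).**

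| Configuration | Between-group variance | λ | Power | n per group for 80% |
|---|---|---|---|---|
| 0, 0, 1.66 | 1.66²/3 = 0.9185 | 7.60 | 64.1% | 13.7 |
| 0, 0.83, 1.66 | 0.83² = 0.6889 | 5.70 | 51.2% | 17.9 |

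These are the plan's own independent-groups model with a consistent input. They are not forecasts for the paired study.

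**4. Precision of one paired technique-minus-caliper difference.** Assumptions: SD 1.555 for every method, one value per mandible and method, and correlation r (not in the documents). SD of the difference = 1.555 × √(2(1 − r)); 95% half-width = t(9) × SD/√10, with t(9) = 2.262.

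| r | SD of difference | 95% half-width (mm) |
|---|---|---|
| 0 | 2.199 | 1.57 |
| 0.5 | 1.555 | 1.11 |
| 0.8 | 0.984 | 0.70 |
| 0.9 | 0.695 | 0.50 |

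**5. Paired power depends on two unknowns.** Paired t-test, n = 10, alpha 0.05.
- Varying r, with an assumed difference of 1.66 mm: 57% (r = 0), 72% (0.3), 85% (0.5), 99.7% (0.8). Under that assumed difference, 80% is reached at r of about 0.43.
- Varying the difference, with r = 0.8: 99.7% for 1.66 mm, 82% for 1.0 mm, 30% for 0.5 mm.

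**The case against.** The strongest reply is that the plan claims less than it is being charged with. It ties 80% to the null of equal group means, which is the omnibus null of the R call, and never to a comparison of one technique with the caliper. That stands. A reader might infer that the plan promises 80% power for each technique against the caliper, but the text does not say so.

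It is also fair that the third group is easily inferred. The Methods describe exactly three sets of measurements, so the unlabelled groups and the loose gloss about radiographic techniques are wording points.

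Next, nothing shows that 1.66 mm is a technique-minus-caliper difference. Part D describes its source data as differences between radiographic techniques and does not label the two means. Paired powers at 1.66 mm, and the correlation of about 0.43, therefore rest on an assumed effect as well as an assumed correlation. The half-widths need no assumed effect.

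Finally, all methods measure the same marked bones, and the documents give no reason to think a correlation near zero realistic. The low-correlation rows are bounds and should not be read as expectations.

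None of this removes the mismatch between two means and three groups, the independence assumption in a paired design, or the absence of a stated analysis for the announced comparison.

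**Conclusion.** The point holds in this form: the 80% claim for 10 mandibles is not supported by the inputs given for it and does not address the comparison in the title. The arithmetic is reproducible, but it needs a spread of 2.03 to 2.35 mm among three means where the plan supplies 1.66 mm between two. With 1.66 mm as the range, the same model gives 64% or 51%. That result assumes the plan's within-group variance, independent groups, and a third mean that lies within the range of the two supplied.

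A reader might go further and infer that 10 mandibles are too few. The documents do not support that. A paired analysis could be precise, with a half-width of 0.70 mm at r = 0.8, or much less so, with 1.57 mm at r = 0. The plan gives neither the correlation nor the difference that matters, so adequacy is not shown either way. The plan should be corrected on this point; the number of mandibles need not change on this evidence.

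**What to change.** 1. Make the paired differences CBCT minus caliper and panoramic minus caliper, on the same 10 mandibles, the main analysis. List the distances to be measured, since the Methods name landmarks but no distances. State how the two readers' two readings are combined, for example as the mean of the four. Report each mean difference with its 95% confidence interval, and say whether any adjustment is made for the number of comparisons. Limits of agreement are optional.
2. Withdraw the 80% claim. In its place give the expected 95% half-width of a paired difference at n = 10 under stated assumptions: with SD 1.555 mm and r = 0, 0.5, 0.8 and 0.9, it is 1.57, 1.11, 0.70 and 0.50 mm. Label any power that is quoted as conditional on both an assumed difference and an assumed r.
3. Label the two input means and name the caliper as the reference in the hypothesis.

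**Cost.** No extra mandibles, images or readings are needed. This is more than rewording: the plan gains a specified main analysis, a list of distances and a rule for combining readings, and it gives up an unconditional power figure. If limits of agreement are added, 10 mandibles estimate them loosely. At r = 0.8 they lie 1.96 × 0.984 = 1.93 mm either side of the mean difference, and each has a 95% half-width of 2.262 × 0.984 × √(1/10 + 1.96²/18) = 1.25 mm.
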